8.5. Electrocardiograms

Twelve-lead ECGs will be obtained for each subject during the study in accordance with Table 12 in Protocol Amendment 10. The baseline for each parameter is the average of all available values collected at screening, Day -1, and Day 1 predose. A table of clinically significant ECG abnormalities and a listing of 12-lead ECG values will be reported in the abbreviated CSR. Electrocardiogram results will be reviewed for clinically notable

abnormalities according to predefined criteria (see Table 12). Number and percentage of subjects with alert ECG values (outliers), defined as the absolute value outside the defined range (see Table 12) and percentage change from baseline greater than 25% (30% for QRS interval), will be summarized.

Parameter	High Threshold	Low Threshold
QTcF ^a	> 460 msec	< 295 msec
PR	> 220 msec	< 75 msec
QRS	> 120 msec	< 50 msec
QT	> 500 msec	< 300 msec
RR	> 1500 msec	< 600 msec

 Table 12:
 Criteria for Clinically Notable Electrocardiogram Abnormalities

^a QTcF (Fridericia correction).

9. INTERIM ANALYSES

9.1. Overview of Interim Analysis

No planned interim analysis for efficacy or futility will be conducted in this study.

9.2. Guidelines for Decision Rules

An interim safety analysis is planned for Phase 2 after 20 subjects have been enrolled and treated for 9 weeks, and then every 3 months thereafter. If the following is reported during these reviews, then enrollment of subjects would be suspended until the sponsor(s), investigators, and regulatory authorities, if applicable, have determined the appropriate course of action:

• > 40% of subjects have had an AE \geq Grade 3 that was attributable to the investigational agent.

Based on these rules, the probabilities of stopping a treatment group for safety is provided in Table 13.

 Table 13:
 Probability of Early Termination for Various Safety Event Rates

Proportion of Subjects Having an AE ≥ Grade 3 That Was Attributable to the Investigational Agent	Probability of Early Termination Based on an AE ≥ Grade 3 That Was Attributable to the Investigational Agent ^{ab}
5%	0.0%
10%	0.1%
15%	0.6%
20%	3.3%
25%	10.2%
30%	23.3%
40%	80.7%

^a Assumes the interim safety analyses occur when enrollment is 20, 80, 160, 240, and 276, etc, subjects. Probability estimated via simulation with 100,000 replications.

^b The probability of early termination = Prob (($\geq 40\%$ of subjects in the active treatment group have had an AE \geq Grade 3 at the first interim safety analysis OR at the second interim OR at the third interim OR at the fourth interim).

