**Phase 2 Cohort Expansions:**

The purpose of the cohort expansions is to gather additional safety, tolerability, preliminary efficacy, [REDACTED] information regarding the combination of INCB024360 and MK-3475 200 mg. Once the safety profile of all doses tested has been characterized and the RP2D of combined administration of INCB024360 and MK-3475 has been defined, the cohort expansions will be initiated at the RP2D (determined in Phase 1 to be 100 mg BID). Fourteen expansion cohorts will be restricted to NSCLC (2 cohorts: PD-L1 positive and PD-L1 low/negative or indeterminate), melanoma (3 cohorts: checkpoint-naïve, primary refractory, and relapsed), transitional cell carcinoma of the GU tract, TNBC, SCCHN, ovarian cancer, DLBCL, MSI high CRC, clear cell RCC, gastric cancer, and HCC. Continuous evaluation of toxicity events in the cohort expansions will be performed throughout enrollment in the expansion cohorts. If the rate of DLTs exceeds 40%, the findings will be reviewed and further enrollment may be interrupted until the sponsor(s), investigators, and regulatory authorities, if applicable, have determined the appropriate course of action. If an expansion cohort is discontinued due to toxicity, a new cohort may be initiated at a previously tested lower dose level.

In each of the cohorts, approximately 18 to 42 subjects will be enrolled to allow for a more precise estimate of ORR in subjects with these tumors and determine whether a target response rate (20%-62%) is likely.

Tumor Type	Approximate No. of Subjects Enrolled
NSCLC high positive (PD-L1 TPS $\geq$ 50%) a	42
NSCLC low/negative or indeterminate (PD-L1 TPS 0%-49% or indeterminate) b	25
Melanoma (immune checkpoint naïve)	40
Transitional cell carcinoma of the GU tract	36
TNBC	32
Ovarian cancer	33
SCCHN	32
DLBCL a	37
RCC	36
MSI high CRC a	29
Gastric cancer	27
HCC a	32
Melanoma (primary refractory) a	27 c
Melanoma (relapsed) a	18 c
Total	446 d

a These cohorts were discontinued before full enrollment.

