### **1.3.3. Risks for the Combination of INCB024360 and MK-3475**

The combination of INCB024360 and MK-3475 has the potential to cause more frequent, more severe, and/or new immune-related toxicities as compared with each individually.

In this ongoing Phase 1/2 study combining pembrolizumab and epacadostat, preliminary data suggest that doses up to 300 mg BID of epacadostat are well tolerated with pembrolizumab 200 mg IV. While 300 mg BID did not exceed the MTD, preliminary analysis of 19 subjects suggested that there were higher rates of dose holds and reductions compared to 100 mg BID, supporting 100 mg BID as the Phase 2 dose (as detailed later in this section). In the Phase 1 portion of the study, a DLT of Grade 3 rash and Grade 3 arthralgia were seen in 2 of 19 evaluable subjects treated with epacadostat 50 mg BID; 2 DLTs in 15 evaluable subjects were seen with epacadostat 100 mg BID (Grade 3 AST and Grade 2 nervous system disorder,

other – ataxia), and 4 DLTs in 19 evaluable subjects were seen at 300 mg BID (Grade 1 erythema, 2 Grade 3 rashes and 1 nervous system disorder – other – vomiting without nausea).

Among the 294 subjects who have received epacadostat 100 mg BID in combination with pembrolizumab in Phase 2, the most frequently reported ( $\geq 5\%$ ) treatment-related AEs were fatigue (29%), rash (17%), nausea (11%), pruritus (10%), diarrhea (8%), decreased appetite (7%), and arthralgia (6%). Rash (17%) noted above includes the following preferred terms: rash, rash maculopapular, rash generalized, rash pruritic, and rash macular. Grade 3 or higher treatment-related AEs were reported in 18% of subjects. Treatment-related AEs leading to treatment discontinuations occurred in 11 subjects (4%); the most common were arthralgia and rash (n = 2 subjects each); others occurred in 1 subject each. There was 1 treatment-related death due to respiratory failure (secondary to aspiration pneumonia; pneumonitis could not be ruled out).

Any treatment-related Grade 3/4 AEs occurring in more than 1 subject included lipase increased (n = 12, 4%), rash (n = 9, 3.0%); fatigue, diarrhea, amylase increased (n = 4 each, 1%); ALT increased and AST increased (n = 2 each, 1%) (Hamid et al 2017).

As noted in Section 1.1.4, the eDMC review of the Phase 3 randomized study ECHO-301/KEYNOTE-252 study noted the safety profile observed was consistent with that observed in previously reported studies of INCB024360 in combination with MK-3475.

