## 9.6. Interim Safety Analyses

An interim safety analysis is planned for Phase 2 after 20 subjects have been enrolled and treated for 9 weeks, and then approximately every 3 months thereafter. If the following is reported during these reviews, enrollment of subjects would be suspended until the sponsor(s), investigators, and regulatory authorities, if applicable, have determined the appropriate course of action:

- > 40% of subjects have had an AE  $\geq$  Grade 3 that was attributable to the investigational agents.

Based on these rules, the probabilities of stopping a treatment group for safety is provided in [Table 22](#).

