5.2. Treatment Groups

Subjects will be summarized overall and based on the dose regimen initially assigned:

- Pembrolizumab 2 mg/kg Q3W intravenously (IV) + epacadostat 25 mg BID
- Pembrolizumab 2 mg/kg Q3W IV + epacadostat 50 mg BID
- Pembrolizumab 2 mg/kg Q3W IV + epacadostat 100 mg BID
- Pembrolizumab 200 mg Q3W IV + epacadostat 300 mg BID
- Pembrolizumab 200 mg Q3W IV + epacadostat 50 mg BID (safety expansion)
- Pembrolizumab 200 mg Q3W IV + epacadostat 100 mg BID (safety expansion)
- Pembrolizumab 200 mg Q3W IV + epacadostat 300 mg BID (safety expansion)
- Pembrolizumab 200 mg Q3W IV + RP2D epacadostat (NSCLC PD-L1 high positive)
- Pembrolizumab 200 mg Q3W IV + RP2D epacadostat (NSCLC PD-L1 low/negative or indeterminate)
- Pembrolizumab 200 mg Q3W IV + RP2D epacadostat (Melanoma immune checkpoint-naive)
- Pembrolizumab 200 mg Q3W IV + RP2D epacadostat (Melanoma primary refractory)
- Pembrolizumab 200 mg Q3W IV + RP2D epacadostat (Melanoma relapsed)
- Pembrolizumab 200 mg Q3W IV + RP2D epacadostat (GU)
- Pembrolizumab 200 mg Q3W IV + RP2D epacadostat (TNBC)
- Pembrolizumab 200 mg Q3W IV + RP2D epacadostat (Ovarian cancer)
- Pembrolizumab 200 mg Q3W IV + RP2D epacadostat (SCCHN)
- Pembrolizumab 200 mg Q3W IV + RP2D epacadostat (DLBCL)
- Pembrolizumab 200 mg Q3W IV + RP2D epacadostat (RCC)
- Pembrolizumab 200 mg Q3W IV + RP2D epacadostat (MSI-high CRC)
- Pembrolizumab 200 mg Q3W IV + RP2D epacadostat (Gastric cancer)
- Pembrolizumab 200 mg Q3W IV + RP2D epacadostat (HCC)

Table summaries, unless otherwise indicated, will be provided by treatment group or tumor type.

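### The Phase 2 40% safety rule states no denominator, and SAP Table 13, labelled as stopping a treatment group, is a pooled calculation that does not follow the rule's own threshold

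*SAP*

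**What the plan says.** Protocol 9.6 (repeated in 5.5.3) and SAP 9.2 suspend enrollment pending review if "> 40% of subjects have had an AE" of Grade 3 or higher attributed to the investigational agents. On timing, Protocol 9.6 says "An interim safety analysis is planned for Phase 2 after 20 subjects have been enrolled and treated for 9 weeks", with reviews about every 3 months after that. Neither document says whether the percentage is taken over all Phase 2 subjects or within a cohort.

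SAP 9.2 then says that "the probabilities of stopping a treatment group for safety is provided in Table 13". Footnote a to that table gives the look schedule: "Assumes the interim safety analyses occur when enrollment is 20, 80, 160, 240, and 276, etc, subjects". Footnote b defines the event as at least 40% "of subjects in the active treatment group have had an AE" at any of four interims. SAP 5.2 lists every Phase 2 tumor cohort as its own treatment group; the HCC entry begins "Pembrolizumab 200 mg Q3W IV + RP2D epacadostat (HCC". Planned cohort sizes run from 18 to 42 (Protocol Table 21, SAP Table 4).

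The Protocol foresees action on a single cohort: "If an expansion cohort is discontinued due to toxicity, a new cohort may be initiated at a previously tested lower dose level". Section 1.3.3 reports on 294 Phase 2 subjects: "Grade 3 or higher treatment-related AEs were reported in 18% of subjects". Section 8.8 provides for no formal data monitoring committee and relies on Section 9.6 for Phase 2 safety.

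**The concern.** The label on Table 13 and the calculation behind it concern different populations. A reader of SAP 9.2 would take the table as a property of each tumor cohort, but no cohort can reach 80 subjects, let alone 276. The footnote threshold (at least 40%) also differs from the rule (more than 40%). Footnote a lists five or more looks while footnote b counts four.

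The denominator matters because the cohorts opened at very different times. HCC and gastric cancer were added by Amendment 7 (15 FEB 2017) and the two PD-1-pretreated melanoma cohorts by Amendment 8 (30 AUG 2017). If the percentage is pooled, excess toxicity in a late cohort is diluted by everyone already enrolled. If it is per cohort, a first look at 20 subjects never arrives in relapsed melanoma (maximum 18). A report that the rule never fired could then be misread as showing that every cohort was monitored and found tolerable.

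**Working it through.** **1. Reproducing Table 13.** Take one pooled sample with true event rate p. At each look, stop if events/n meets the threshold; otherwise add the next binomial increment and continue (exact recursion). Looks are at 20, 80, 160, 240 (four) or also 276 (five).

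| True rate | SAP Table 13 | At least 40%, 4 looks | More than 40%, 4 looks | Protocol Table 22 |
|---|---|---|---|---|
| 10% | 0.1% | 0.04% | 0.01% | 0.04% |
| 15% | 0.6% | 0.59% | 0.13% | 0.58% |
| 20% | 3.3% | 3.22% | 1.00% | 3.17% |
| 25% | 10.2% | 10.26% | 4.15% | 10.35% |
| 30% | 23.3% | 24.09% | 12.47% | 24.31% |
| 40% | 80.7% | 82.35% | 73.02% | 85.37% |

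The pooled calculation with footnote b's threshold matches every row of Table 13 within 2 points. The closest fit uses at least 40% at the first look, more than 40% afterwards, and five looks: 23.47% and 80.96% in the last two rows. The rule as written in the text does not reproduce the table; a fifth look raises its last row only to 75.45%. Table 22 states no look schedule. Its 40% row is nearer to five looks at the at-least threshold (83.39%) and differs from Table 13 by 85.37 − 80.7 = 4.7 points.

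**2. The pooled reading applied to a late cohort.** Inputs: 294 Phase 2 subjects as of 27 FEB 2017 and 18% with a Grade 3 or higher treatment-related AE (Protocol 1.1.4, 1.3.3); HCC planned at 32 (Table 21).

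- Background events: 0.18 × 294 ≈ 53.
- Every HCC subject has an event: (53 + 32)/(294 + 32) = 85/326 = 26.1%.
- Needed to exceed 40% of 326 (130.4): 131 events, so 131 − 53 = 78 from 32 subjects, which is impossible.

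**3. Where that result stops holding.**

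- Early enrollment: with N other subjects at 18%, 32 of 32 exceeds 40% when (32 + 0.18N)/(32 + N) > 0.40, so N < 19.2/0.22 = 87.3, or at most 87 others.
- Higher background rate b: 32 + 294b > 130.4 gives b > 98.4/294 = 33.5%.

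**4. What a within-cohort rule would deliver, for scale.** The more-than-40% rule needs 5 or more events of 10, or 9 or more of 20.

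| Looks | True 50% | True 60% |
|---|---|---|
| 10 only (all that an 18-subject cohort reaches) | 62% | 83% |
| 10 and 20 | 80% | 96% |

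**The case against.** The strongest reply is that the rule no longer operates. Its only action is to suspend enrollment, SAP 10.1 records that enrollment ended permanently on 17 MAY 2018, and this SAP version is dated 17 MAY 2019. That stands, and it removes any claim that a correction would protect subjects now. What remains is a mislabelled table and how the rule is reported.

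Second, the useful retrospective output is already planned. SAP 8.2.2 summarizes Grade 3 or higher treatment-related TEAEs by treatment group, which means by cohort. That also stands; only the comparison with 40% is missing.

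Third, there is another trigger: Protocol 4.1.2 and SAP 3.2 call for continuous toxicity evaluation in the expansion cohorts, with review if the DLT rate exceeds 40%. It is a separate trigger, but it does not resolve the point. Its denominator is also unstated, Protocol 5.5.1 defines DLTs for Phase 1, and Protocol 4.1.2 refers the reader back to Section 9.6.

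A reader might go further than the documents allow in three ways:

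- *That the rule is computed on pooled data and one cohort can never trigger it.* The rule text names no denominator, the wording about treatment groups points toward cohorts, and step 3 shows that never is conditional.
- *That all four late cohorts together could not trigger it.* With an event in each of their 104 planned subjects, (53 + 104)/(294 + 104) = 157/398 = 39.4%. Three more background events give 160/398 = 40.2%. The safety update required only 1 month of data, so the background count could rise.
- *That the late cohorts were expected to be more toxic.* For single-agent PD-1 inhibitors the Protocol reports Grade 3 or 4 related AE rates of 13% in gastric cancer and 17% in HCC, no higher than 18%, and gives no rate for PD-1-pretreated melanoma on the combination.

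**Conclusion.** The point holds as an inconsistency in the plan. The denominator of the 40% rule is undefined. Table 13 gives pooled probabilities under a treatment-group label, so they describe no treatment group. It also uses a threshold that the rule text does not: at a true rate of 30% the stated 23.3% is nearly double the 12.5% that the written rule gives. Tables 13 and 22 disagree with each other at 40%.

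The dilution result (26.1% at most for HCC) is conditional on the pooled reading, on 18% being a proportion of the 294, on essentially none of those 294 being HCC subjects, and on treatment-related and attributable meaning the same thing. The figure of 32 is the planned size, and HCC closed before full enrollment. It does not show that the trial lacked all cohort-level oversight.

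Severity is minor to moderate. Calling it a must-fix would not be supported, because enrollment is closed and the by-cohort safety table is already planned.

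**What to change.** 1. In Protocol 9.6 (and 5.5.3) and SAP 9.2, reconcile the passages by stating the denominator (pooled, per cohort, or both) and one threshold (more than, or at least). The choice is the sponsor's.
2. Relabel Tables 13 and 22 as pooled Phase 2 probabilities, recompute both under that single rule, and give one look schedule and one number of looks.
3. If cohort-level protection is claimed, add cohort-level probabilities using looks that each cohort can reach. Five cohorts (18, 25, 27, 27 and 29 subjects) never reach 30, so a schedule of 10, 20 and 30 would overstate what they get.
4. In the CSR, set the by-treatment-group Grade 3 or higher treatment-related TEAE rates from SAP 8.2.2 against 40%, and do not cite the untriggered pooled rule as evidence that each cohort was tolerable.

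The cost is wording, two recomputed tables and one reference value beside an existing output. A prospective cohort-level rule would also raise more flags. With looks at 10, 20 and 30 and a true rate of 18%, each cohort is flagged with probability 2.4%, so at least one of 14 is flagged with probability 1 − (1 − 0.024)^14 ≈ 29%. That is an upper figure, since some cohorts have fewer looks, and each flag leads to a review, not to termination.

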10. CHANGES AND MODIFICATIONS TO THE ANALYSIS PLAN

All versions of the SAP are listed in Table 14.

SAP Version	Date
Original	22 DEC 2014
Amendment 1	27 JUL 2016
Amendment 2	21 AUG 2017
Amendment 3	08 MAR 2018
Amendment 4	17 MAY 2019

Table 14:Statistical Analysis Plan Versions

10.1. Changes to Protocol-Defined Analyses

Study enrollment was permanently discontinued on 17 MAY 2018 as a strategic decision. This decision was made following the recommendation of the external Data Monitoring Committee of the INCB 24360-301 blinded melanoma clinical study, which determined that the study did not meet the prespecified endpoint of progression-free survival improvement for the combination of pembrolizumab + epacadostat compared with pembrolizumab + placebo; in addition, the overall survival (OS) endpoint was not expected to reach statistical significance. Of note, there were no new safety concerns identified in either arm of the melanoma study.

Due to this strategic decision, Protocol-defined analyses were reduced. Efficacy analyses will only be performed for primary and secondary endpoints

See Appendix E for a detailed list of outputs that will be included in the abbreviated CSR for both safety and efficacy.

10.2. Changes to the Statistical Analysis Plan

10.2.1. Original to Amendment 1

The purpose of SAP Amendment 1 was to coincide with changes in Protocol Amendment 5: to replace the randomized, placebo-controlled portion of the study conducted in subjects with NSCLC with an open-label expansion in subjects with select cancers including melanoma, transitional cell carcinoma of the GU tract, TNBC, ovarian cancer, SCCHN, DLBCL, clear cell RCC, and 2 cohorts of subjects with NSCLC based on PD-L1 expression.

10.2.2. Amendment 1 to Amendment 2

The purpose of SAP Amendment 2 is to coincide with changes in Protocol Amendments 6 and 7: to add MSI-high CRC, gastric cancer, and HCC expansion cohorts to Phase 2 of the study. Additionally, the list of sponsor-defined AEOSIs was updated.

10.2.3. Amendment 2 to Amendment 3

The main purpose of SAP Amendment 3 is to coincide with changes in Protocol Amendments 8 and 9: to add melanoma (primary refractory) and melanoma (relapsed) expansion cohorts to Phase 2 of the study. The list of sponsor-defined AEOSIs and ECIs were updated. Some treatment-related safety tables have been removed. Additionally, the subgroup analyses were modified per each tumor type.

10.2.4. Amendment 3 to Amendment 4

The purpose of SAP Amendment 4 is to reflect changes in wording from Protocol Amendment 10, remedy sections with lack of clarity on Protocol-defined analyses, reflect updates to the overall AE summary table, and make transparent what will be reported in the abbreviated CSR. Additionally, the list of sponsor-defined AEOSIs was updated.

A population PK model of epacadostat has been developed based on data from multiple epacadostat Phase 1, 2, and 3 studies (DMB-18.142.1).

11. **REFERENCES**

DMB-18.142.1. Population Pharmacokinetic Analysis of the IDO1 Inhibitor Epacadostat (INCB024360) Tablets Administered Orally to Healthy Participants and Various Cancer Patient Populations (With Respect to Merck Collaboration). Wilmington, DE: Incyte Corporation. Approval date: 06 MAY 2019.

Food and Drug Administration (FDA). Guidance for Industry: Clinical Trial Endpoints for the Approval of Cancer Drugs and Biologics. 2007.

APPENDIX A. CLINICAL LABORATORY TESTS

Serum Chemistry	Hematology	Other
Albumin Alkaline phosphatase ALT AST Amylase Bicarbonate Blood urea nitrogen Calcium	Complete blood count, including: • Hemoglobin • Hematocrit • Platelet count • Red blood cell count • Reticulocyte count • White blood cell count	Serology: Hepatitis B surface antigen Hepatitis B surface antigen antibody Hepatitis B core antibody Hepatitis C virus antibody HCV-RNA HBV-DNA Pregnancy test:
Chloride Creatinine Glucose Iron Lactate dehydrogenase Phosphorus Potassium Serum or plasma lipase Sodium Total bilirubin Direct bilirubin (if total bilirubin is elevated above ULN) Total protein Uric acid	Differential count, including: • Basophils • Eosinophils • Lymphocytes • Monocytes • Neutrophils	Female subjects of childbearing potential only require a serum test at screening. Pregnancy tests (serum or urine) should be repeated if required by local regulations. Urinalysis with microscopic examination: Color and appearance pH and specific gravity Bilirubin Glucose Ketones Leukocytes Nitrite Occult blood Protein Urobilinogen Coagulation: PT aPTT INR
Lipid Panel	Standard LFT Monitoring	Endocrine Monitoring
Total cholesterol Triglycerides LDL HDL CRP	Alkaline phosphatase ALT AST Total bilirubin	ACTH Serum cortisol (9 AM) ^a LH ^b Prolactin TSH Free thyroxine (T4) Total triiodothyronine (T3) Serum testosterone (9 AM) ^c

ACTH = adrenocorticotropic hormone; ALT = alanine aminotransferase; aPTT = partial thromboplastin time; AST = aspartate aminotransferase; CRP = C-reactive protein; DLCO = diffuse lung capacity for carbon monoxide; $FEF_{25\%-75\%}$ = forced expiratory flow 25% to 75%; FEV_1 = forced expiratory volume in 1 second; FVC = forced vital capacity; HBV-DNA = hepatitis B virus deoxyribonucleic acid; HCV-RNA = hepatitis C virus ribonucleic acid; HDL = high-density

lipoprotein; IgG = immunoglobin G; INR = international normalized ratio; LDL = low-density lipoprotein; LFT = liver chemistry tests; LH = luteinizing hormone; PEF = peak expiratory flow; PT = prothrombin time; TSH = thyroid-stimulating hormone; ULN = upper limit of normal; VA = alveolar volume.

^a Serum cortisol ideally should be drawn close to 9 AM but can be done any time before noon.

^b Not needed in women, surgically castrated men, or men taking LH-releasing hormone agonist therapy.

^c Not needed in subjects taking testosterone replacement therapy.

